13.0 PHOTOGRAPHY

Standardized and 3D photographs will be taken of the treatment area. Photographs will be taken with an appropriate high-resolution digital camera. Camera settings (lighting, distance, background, polarization, etc.) will be reproduced at

each visit, so that photographs are suitable for comparison. Photographs will be taken of the treatment area for study purposes. If the subject does not wish to have their photographs taken, they cannot be in the study.

14.0 ADVERSE REACTIONS DEFINITIONS AND REPORTING REQUIREMENTS

All adverse events that occur, starting from the time of the first treatment, will be recorded in the source documents and Case Report Forms (CRF).

Adverse Events (AE) occurring will be captured and followed until the condition resolves, stabilizes, is otherwise explained, or the subject is lost to follow-up. Subjects will be instructed that they may contact the Investigator at any time throughout the course of the study.

The Investigator and/or designated study staff will review each event and assess its relationship to the study device (not related, unlikely, possible, probable, and highly probable). The following definitions will be used for rating relationship to the TempSure® Firm treatments:

- Not related – The event is clearly related to other factors such as the subject's clinical state, therapeutic interventions, or concomitant medications administered to the subject.
- Unlikely – The event was most likely produced by other factors such as the subject's clinical state, therapeutic interventions, or a concomitant medication administered to the subject; and does not follow a known response pattern to the investigational product.
- Possible – The event follows a reasonable temporal sequence from the time of investigational product administration; **and/or** follows a known response pattern to the study sampling sessions; **but** could have been produced by other factors such as the subject's clinical state, therapeutic interventions, or concomitant medications administered to the subject.
- Probable – The event follows a reasonable temporal sequence from the time of investigational product administration; **and** follows a known response pattern to the investigational product; **and** cannot be reasonably explained by other factors such as the subject's clinical state, therapeutic interventions, or concomitant medications administered to the subject.
- Highly Probable – The event follows a reasonable temporal sequence from the time of investigational product administration; **and** follows a known response pattern to the investigational product; **and** cannot be reasonably explained by other factors such as the subject's clinical state, therapeutic interventions, or concomitant medications administered to the subject; **and** either occurs immediately following investigational product administration, **or** improves on stopping the investigational product, **or** reappears on repeat exposure, **or** there is a positive reaction at the application site.

Each adverse event reported will be graded on a 3-point severity. Using the following definitions for rating severity will be used:

- Mild – easily tolerated, causing minimal discomfort, and not interfering with normal everyday activities.
- Moderate – sufficiently discomforting and may interfere with normal everyday activities.
- Severe – incapacitating and/or preventing normal everyday activities.

A Serious Adverse Event (SAE) is any adverse device experience that results in any of the following outcomes: death, a life-threatening adverse device experience, in-patient hospitalization or prolongation of hospitalization, a persistent or significant disability/incapacity, or a congenital anomaly/birth defect. Important medical events that may or may not result in death, be life-threatening, or require hospitalization may be considered a serious adverse device experience when, based upon appropriate medical judgment, they may jeopardize the subject or subject may require medical or surgical intervention to prevent one of the outcomes listed in this definition

If any of the above adverse events are serious as defined by the FDA Code of Federal Regulations (CFR), Title 21, special procedures will be followed. All serious adverse events will be reported within 24 hours of acknowledgment to the Sponsor whether or not the serious events are deemed sampling session-related. All serious event reporting will adhere to 21 CFR part 812 and the IRB will be notified accordingly.

The SAE information will be entered into the database and a desk copy of the complete SAE report will be submitted to the study file.

Adverse events, whether serious or non-serious, will be followed until the condition is resolved, stabilized, otherwise explained or the subject is lost to follow-up. Adverse events will be captured throughout the study and where appropriate, medical tests and examinations will be performed to document the resolution of event(s). Outcomes may be classified as resolved, improved, unchanged, worse, fatal, unknown or lost to follow-up. Following the resolution of any study-associated adverse events there will be no further adverse event reports for that subject.

Reporting Adverse Events:

Report	Submit To	Description/Constraints
Adverse Events, Unanticipated Adverse Device Effect	IRB and Sponsor	If an unforeseen complication is determined to be an unanticipated adverse device effect, the investigator's report must be submitted within 10 working days after the investigator first learns of the effect.
Serious Adverse Events	IRB and Sponsor	The sponsor must be notified within 24 hours of serious adverse events. The IRB must be notified within 10 working days of serious adverse events as defined by FDA guidelines.

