2.7 Treatment Procedures

- The Investigator will use the device as described in the TempSure Operator's Manual and Clinical Reference Guide.
- Gel will be applied to the treatment area.
- The TempSure® Firm handpiece (25mm, 30mm, 60mm) to be used and the limits of the area to be treated will be determined by the Investigator and will be used in accordance with the Tempsure Clinical Reference Guide.
- The handpiece will be placed in contact with the skin.
- The entire defined treatment area will then be treated by delivering energy to the skin.
- Parameters may be adjusted throughout the treatment to increase subject comfort.
- Subjects will be asked to report the general level of treatment discomfort/pain on a scale of 0 (none) to 10 (maximum intolerable pain).

- Temperature will be continuously monitored and recorded during treatment.
- Photographs may be taken at any time during treatment to document treatment area and any adverse events, if applicable.
- Subjects may receive up to 5 treatments every 1-2 weeks.
- The additional treatments will follow the same procedure.
- Adverse Events will be documented at all treatment visits.

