2.8 Post Treatment Procedures

- Adverse events will be documented after treatment.
- Post treatment instructions will be reviewed.
- Photographs may be taken.

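### Section 14.0 ends adverse event reports for the whole subject once a study-associated event resolves; taken literally this contradicts the protocol's other adverse event rules, and the sentence should be deleted or limited to the resolved event

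*Combined protocol and SAP*

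**What the plan says.** The sentence at issue closes the follow-up paragraph of section 14.0: "Following the resolution of any study-associated adverse events there will be no further adverse event reports for that subject". The trigger is resolution of a study-associated event, so resolution of an unrelated event does nothing. *Reports* is not defined.

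Other text on recording:
- Same paragraph, two sentences earlier: "Adverse events will be captured throughout the study".
- Opening of section 14.0: "All adverse events that occur, starting from the time of the first treatment, will be recorded".
- Section 2.7: "Adverse Events will be documented at all treatment visits".
- Section 2.8: "Adverse events will be documented after treatment".
- Section 2.9 has a call after each treatment to record side effects, and adverse event documentation at both follow-up visits.
- The schedule in section 2.12 marks an adverse event assessment at every visit and call.
- Section 2.15.6 bases the safety assessment on adverse events collected over the whole study.

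Other text on onward reporting, all in section 14.0:
- "All serious adverse events will be reported within 24 hours of acknowledgment to the Sponsor". The table below the disputed sentence repeats the 24-hour limit and adds notice to the IRB within 10 working days.
- The same table requires a report to the IRB and sponsor within 10 working days: "If an unforeseen complication is determined to be an unanticipated adverse device effect".

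None of these rules makes an exception for a subject whose earlier event has resolved.

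**The concern.** Treatments are repeated, up to 5 at intervals of 1 to 2 weeks. Section 2.14 expects mild discomfort, swelling and redness to clear typically within 2 to 24 hours. The trigger could therefore be met after the first treatment, with up to 4 treatments and both follow-up visits still to come.

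Safety through adverse event collection is a secondary objective (section 1.1), and an acceptable side effect profile is a success criterion (section 2.15.1). Section 3.3 says that safety data for this indication are limited. If a site took the sentence as a rule for recording, a later event of a different type or greater severity in that subject would be missing from the counts and percentages of patients by outcome in section 2.15.6. If a site took it as a rule for onward reporting, it would face two instructions that cannot both be followed for a later serious or unanticipated event.

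**Working it through.** The plan states no figure to reproduce. The check sets the sentence against the other text under each meaning of *reports*, then counts scheduled contacts.

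**1. *Reports* as follow-up reports on the resolved event, or as close-out after the study.** No conflict. Section 14.0 already follows each condition until it resolves, stabilizes or is otherwise explained. But the sentence names the subject and not the event, and it does not mention the end of the study.

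**2. *Reports* as onward reports to the sponsor and IRB.** This is the better-supported sense of the noun: section 14.0 speaks of an SAE report, and the table directly below the sentence lists reports and their recipients. Case report form recording survives. The sentence then conflicts with the 24-hour rule for serious events and the 10-working-day rule for unanticipated device effects. No explicit deadline exists for non-serious, anticipated events, so the direct contradiction is confined to those two rules. The sponsor's review of documented events in section 2.14 is not a conflict, because it can work from the case report forms.

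**3. *Reports* as recording.** Support is thinner. Section 14.0 uses the verb in a way that can mean this ("Each adverse event reported will be graded on a 3-point severity"), though that may also mean reported by the subject. The sentence would then contradict sections 2.7, 2.8, 2.9, 2.12 and 2.15.6, the opening of section 14.0, and its own paragraph.

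**4. *Any* read as *all*.** If this means all of the subject's events to date, the stop is only delayed: a subject can have no open event between treatments. If it means all events over the whole study, the condition cannot be met until participation ends, which is the close-out reading in step 1.

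**5. Count of contacts, meaning 3 only.** Inputs from sections 2.9 and 2.12, for one subject given all 5 treatments: 5 treatment visits + 5 calls + 2 follow-up visits = 12 adverse event contacts from treatment 1 onward. Assumed order: treatment k, call k, treatment k+1. Assumed trigger: a single study-associated event after treatment k.

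- Resolution learned at call k: contacts left = 12 − 2k.
- Resolution known before call k: contacts left = 12 − (2k − 1).

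| Treatment k | Treatments left (5 − k) | Learned at call k | Known before call k |
|---|---|---|---|
| 1 | 4 | 10 of 12 | 11 of 12 |
| 2 | 3 | 8 of 12 | 9 of 12 |
| 3 | 2 | 6 of 12 | 7 of 12 |
| 4 | 1 | 4 of 12 | 5 of 12 |
| 5 | 0 | 2 of 12 | 3 of 12 |

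The call is the next scheduled contact at which a site would learn of resolution, so the third column is the more realistic one. These are contacts, not lost events. Under meanings 1 and 2, no recording contact is lost.

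**The case against.** The strongest defence is that the sentence closes a paragraph about follow-up and is meant as a close-out line. Follow-up to resolution can outlast the last visit, which would explain why a closing line speaks of the subject. On that reading nothing conflicts. This stands as the likely intent, and it rules out saying that every reading leaves a contradiction. It does not rescue the wording, which carries no such limit.

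A second objection is that the protocol uses other verbs (recorded, documented, captured) for case report form entry and keeps the noun *report* for submissions. This also stands. It weakens the recording reading and makes the contact counts illustrative only. It moves the literal conflict to the serious and unanticipated event rules but does not remove it. Those rules are specific and unqualified, so a site is unlikely to let a general closing sentence override them.

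A reader might infer that sites would stop collecting adverse events and that the safety tables would be materially incomplete. The documents do not support that. Most of the adverse event text directs continued collection, and a site following the visit schedule would continue. The percentage of subjects with any adverse event would not change even under the recording reading, because the stop needs an event already on record. Section 2.15.6 plans no statistical comparison, and pain scores are collected separately at each treatment.

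**Conclusion.** Wrong as written, low severity. The sentence puts the stop on the subject where the likely intent concerns the resolved event or the end of participation. Literally, it contradicts the serious and unanticipated event reporting rules if *reports* means onward reports, or the adverse event recording rules if it means recording.

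The effect on the data cannot be sized: the documents give no adverse event rates, and how sites would read the sentence is unknown. It is probably small. The 10 of 12 contacts (11 if resolution is known before the first call) is a worst case. It rests on the less-supported recording reading, all 5 treatments being given, a treatment-1 reaction that resolves, and the stop taking effect at that first resolution. Confidence is high that the wording conflicts, and does not extend to any predicted loss of safety data.

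**What to change.** Delete the sentence; the per-event follow-up rule already in section 14.0 covers the likely intent. Alternatively, reconcile it with the rest of section 14.0 by limiting it to the event, for example: *Once an adverse event has resolved, stabilized or been otherwise explained, no further follow-up reports are needed for that event; new or recurrent events continue to be recorded and reported throughout the subject's participation.*

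The cost is one sentence. Section 21.0 requires written IRB approval for any protocol revision, so the change could be bundled with another amendment. It adds no visit, call or procedure, since adverse events are already assessed at every scheduled contact.

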15.0 PROTOCOL DEVIATIONS

All requests for protocol deviations by the Investigator must be communicated to the sponsor in writing and if accepted by the Sponsor must be approved by the IRB. If a deviation occurs, the Investigator must inform the Sponsor as soon as possible. The Sponsor will notify the IRB in accordance with IRB specific policies.

16.0 CONFIDENTIALITY AND DISCLOSURE OF MEDICAL INFORMATION

As part of this study the Investigator and the team at the research facility will keep records of subject participation in the study. These study records will include personal information that the subjects provide including age, sex, etc., the results of the study, information about response to treatments, photographs taken during the study and other medical information relating to participation in the study.

Under federal law the study records cannot be used or disclosed by the Investigator for research purposes unless subjects sign the informed consent authorization.

Some or all of the test results, photographs and other information will be reported to Cynosure, Inc. the manufacturer of the test device (Sponsor), and consultants that are helping conduct the study. The Sponsor and its consultants will analyze and evaluate these results and information and may report them to the U.S. Food Administration and the FDA, Institutional Review Board or other regulatory agencies in the United States and/or foreign countries. The subject's study records will be assigned a code number by the study team and they will ordinarily not be identified by name in the study records that are sent to the Sponsor and its consultants. However, The Sponsor, the Institutional Review Board and its consultants will have the right to see the complete study records, including the subject's name, and might choose to do so. If reports or articles are written about the study, the subject will not be identified by name in them however your study information and photographs may be used.

The research facility will review and use the study records only for purposes of this study. They will keep the subject's identity confidential and, except for the disclosures described above, will not disclose the study records to other parties

unless disclosure is required by law. Once the research facility discloses information in the study records, photographs or medical records to the Sponsor or its consultants, the information will no longer be protected by federal law. Because of the need to release information to these parties, absolute confidentiality cannot be guaranteed. However, the Sponsor and its consultants will only use information for purposes of the study and will not disclose your study records to parties other than; the FDA or other regulatory agencies in the United States and/or foreign countries, unless disclosure is required by law. If reports or articles are written about the study, subjects will not be identified by name in them however, subject study information and photographs may be used.

Study records will be kept at the research facility according to applicable regulations and policies and may be kept indefinitely following the completion of the study. Subjects will not have the right to review their records while the research is in progress. However, they will be able to review their records after the research has been completed.

17.0 CLINICAL RESEARCH CONDUCT

The study will be conducted in accordance with the protocol, International Conference on Harmonization (ICH) GCP guidelines, applicable regulations and guidelines governing clinical study conduct and ethical principles that have their origin in the Declaration of Helsinki. The investigator must ensure that the study is conducted in accordance with the provisions as stated in the FDA regulations and complies with the applicable local or regional regulatory requirements.

18.0 REPORTING FOR THE STUDY

A study summary report will be generated. It will include a description of the clinical conduct of the study and results.

Study Summary Reporting:

Report	Submit To	Description/Constraints
Deviation from Investigational Plan	IRB and Sponsor	A deviation performed in an emergency to protect the life or physical well-being of a patient necessitates notification of the IRB and sponsor. The investigator's report must be submitted within 5 working days after the emergency occurred. Deviations in a non-emergency situation require notification to sponsor prior to implementation
Failure to Obtain Informed Consent	IRB and Sponsor	The investigator must make notification within 5 working days after device use, using the Protocol Deviation CRF. The report must include a brief description of the circumstances justifying the failure to obtain informed consent.
Final Report	IRB and Sponsor	The investigator must submit a final report within 3 months after termination or completion of the investigation.
Withdrawal of IRB approval	Sponsor	The investigator must report a withdrawal of the reviewing IRB approval within 5 working days .
Progress Report	IRB, Monitor and Sponsor	The investigator must submit progress reports at regular intervals, and as required by the IRB, but in no event less than annually.

19.0 DISCLOSURE

The Principal Investigator and Cynosure employees and consultants have signed confidentiality agreements with the sponsor. This confidentiality agreement ensures that all information provided to the Investigator or Data Management

and Statistics group dealing with the study and information obtained during the course of the study will be regarded as confidential.

20.0 RESPONSIBILITY OF THE INVESTIGATOR

The Investigator is responsible for ensuring that the clinical study is performed in accordance with the International Conference on Harmonization (ICH), Good Clinical Practice (GCP) guidance E6, FDA Good Clinical Practice Regulations, Declaration of Helsinki (DoH) and the Health Human Service (HHS) Belmont Study. Investigators will supply information to the sponsor such that the sponsor can comply with the Financial Disclosure Rules.

21.0 PROCEDURE FOR AMMENDMENTS TO PROTOCOL

No deviations from this protocol will be permitted, except in a medical emergency, without the approval of the Sponsor. Any amendment to this study will be discussed by the Investigator and the Sponsor. If agreement is reached concerning the need for modification, this will be made in a formal amendment to the protocol.

All revisions and/or amendments to the protocol must be approved in writing by the appropriate Institutional Review Board.

22.0 TERMINATION OF STUDY

The Sponsor reserves the right to discontinue this study for administrative reasons at any time. The Investigator reserves the right to discontinue the study for safety reasons at any time in collaboration with the Sponsor.

23.0 DATA SECURITY

To ensure the privacy and confidentiality of data for this protocol, the data will be stored on a restricted access location on a company server. Access to the project directory containing the data will be limited to the Investigators and research staff. Information about data security awareness is promoted through user training and education, supplemented by policies and procedures. Password protection will be used for all transactions that allow viewing, editing, and analysis of data, or that provide access to data fields derived from the original source documents.

24.0 REPORT OF PRIOR INVESTIGATIONS

The report of prior investigations or predicates are:

Protocol	Device	IRB Name	Determination	Initial IRB Approval Date
CYN17-RF-CLINIC	TempSure/Pelleve	Allendale Investigational Review Board	Meets the criteria for exemption from IDE regulations, non-significant risk	01/12/2017
CYN18-RF-TISSUE-RD	TempSure/ Radiofrequency Devices	Allendale Investigational Review Board	Meets the criteria for exemption from IDE regulations, non-significant risk	08/15/2018
CYN19-TS-ABDOM	TempSure	Allendale Investigational Review Board	Meets the criteria for exemption from IDE regulations, non-significant risk	04/11/2019

CYN19-TS-ENVI-ABD	TempSure	New England IRB	Meets the criteria for exemption from IDE regulations, non-significant risk	03/25/2019
-------------------	----------	-----------------	---	------------

